11.1. Definition of Serious Adverse Events

A serious adverse event is any untoward medical occurrence that:

• results in death

- is life-threatening (i.e., an event in which the participant was at risk of death at the time of the event; it does not refer to an event which hypothetically might have caused death if it were more severe).
- requires inpatient hospitalisation or prolongation of existing hospitalisation
- results in persistent or significant disability/incapacity
- consists of a congenital anomaly or birth defect.

Other 'important medical events' may also be considered a serious adverse event when, based upon appropriate medical judgement, the event may jeopardise the participant and may require medical or surgical intervention to prevent one of the outcomes listed above.

NOTE: The term "life-threatening" in the definition of "serious" refers to an event in which the participant was at risk of death at the time of the event; it does not refer to an event which hypothetically might have caused death if it were more severe.

11.2. Reporting Procedures for Serious Adverse Events

The duration of the SAE recording period for each participant lasts from their enrolment on to the study, to their completion of the study. Any serious adverse event (SAE) occurring to a participant will be recorded at the time that the research team is made aware of the incident, and reported to the REC that gave a favourable opinion of the study where in the opinion of the Chief Investigator/clinically qualified member of the study team the event was 'related' (resulted from administration of any of the research procedures) and 'unexpected' in relation to those procedures. Reports of related and unexpected SAEs will be submitted within 15 working days of the Chief Investigator becoming aware of the event, using the HRA report of serious adverse event form, in accordance with HRA process.

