Self-monitoring will be supported by provision of blood pressure and blood glucose monitors for participants to use at home throughout the intervention period. The blood pressure and blood glucose monitors will be sent out via post to participants in the intervention arm following randomisation. These monitors form a key tool for participants to learn and monitor how their weight and diet affect their blood glucose and blood pressure, and will assist their clinicians in assessing their response to the programme and any medication changes. Participants will be given access to a set of instructions as part of the online materials (appendix B) (signposted to by the programme coach) and a printed copy of these sent with the equipment via post, which detail how to use the monitors, and how to interpret the readings should they be unexpectedly high or low, with a traffic light system detailing what action they should take and when they should contact their clinician. Participants will be encouraged to monitor their blood pressure 3 times per week, their blood glucose three times per week (twice a day on these days – once on waking, and once after they have eaten a meal), and to weigh themselves once a week. The coach will ask about the blood pressure, glucose and weight measures during the coaching sessions and these will form a key part of motivating and guiding participants with the intervention.

The programme will include remote coaching sessions at baseline, 2, 4, 8, 12, 16 and 20 weeks to provide support and guidance to the patient to enable them to follow the low-carbohydrate, low-energy intervention (Intervention content shown in appendix B). The participant will receive a text or phone call (depending on the method of contact the participant requests) to organise and schedule the first baseline appointment. All subsequent appointments will be remote and will also be arranged between participants and coach at a day and time convenient for both. In addition, the intervention providers are able to provide additional functionality within their digital offering including access to educational materials, recipe and cooking guides etc (Appendix B). All sessions will be audio-recorded.

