11. SAFETY REPORTING

We considered but decided to not record adverse events, except serious adverse events (see below section 11.1). It is hard to engage people who are in the control group (not a placebo) in recording adverse events, which seems an irrelevance to them, and these participants are also not attending appointments to collect such data. However, we will ask nurses in the intervention arm to record adverse events of special concernnamely episodes of hypoglycaemia or episodes of symptomatic hypotension that required outside assistance to manage, episodes of ketosis, or hospitalisation for international normalised ratio (INR) out of range in people on warfarin.

In addition, at 20 weeks, we will record serious adverse events for all patients, namely episodes of hospitalisation that were not planned at baseline, death or life-threatening event, illness or injury that resulted in permanent significant disability, or resulted in congenital abnormality. In the DiRECT trial, SAEs were less common in the intervention than control group. In our analysis, we will classify SAEs as diabetes-related (macrovascular or microvascular disease) or other. We will not prospectively record SAEs because this type of treatment is known to reduce the incidence of serious disease, and our retrospective recording will be sufficient to add to data on this.

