12.2. Sample size determination

Assuming a mean weight loss of 5kg in the intervention arm and 1kg in the control arm, both with a standard deviation of 3.5 kg, we would need 21 participants per group to detect a difference of 4kg between the groups. To account for dropouts, we will recruit 30 people per group.

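### Sections 11 and 11.2 conflict on how SAEs are recorded; if awareness-based records enter the by-arm summary, ascertainment is unequal and may inflate the intervention count

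*Protocol*

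**What the plan says.** **Two recording rules.** Section 11 states that "at 20 weeks, we will record serious adverse events for all patients". It then disclaims interim capture: "We will not prospectively record SAEs because this type of treatment is known to reduce the incidence of serious disease", and concludes that "our retrospective recording will be sufficient to add to data on this". Section 11.2 sets a recording period from enrolment to completion and says that any SAE "will be recorded at the time that the research team is made aware of the incident". Reporting to the ethics committee is limited to related and unexpected events; the recording clause has no such limit.

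**Contacts in the intervention arm.** Section 10.1 provides "remote coaching sessions at baseline, 2, 4, 8, 12, 16 and 20 weeks", one extra telephone appointment with the GP or practice nurse, session data entered by the coach in the eCRF, and two-way communication between coach and practice. Section 10.6 sends the session recordings to the study team. Section 11 asks nurses in this arm to record special-concern events, among them hospital admission because of an out-of-range INR in people on warfarin.

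**Contacts in the control arm.** Section 10.2 gives usual care only. Section 10.3.1 adds a week-12 link to a food questionnaire, with no SAE question stated. Section 10.3.2 adds the week-20 visit. Section 11 itself remarks of controls that "these participants are also not attending appointments to collect such data".

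**Week 20 and losses.** Section 10.3.2 lists weight, blood pressure, blood tests and questionnaires. It has no SAE item and no source for people who do not return. Section 12.2 says: "To account for dropouts, we will recruit 30 people per group", up from 21.

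**The concern.** Read together, the two sections leave open whether the SAE table rests on one retrospective record taken at the same time in both arms, or on that record plus whatever the team has heard along the way. The second source is lopsided by design, because nearly all the interim routes belong to one arm. One kind of SAE is even actively sought in that arm alone: an unplanned admission for INR is an SAE under section 11.

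The asymmetry matters for SAEs that the week-20 record misses and for participants lost before week 20. Section 10.7 keeps data up to withdrawal unless the participant asks otherwise. An SAE heard about before an intervention participant leaves would therefore stay in the count, while a control who leaves has no comparable scheduled route.

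Section 11 cites fewer SAEs in the intervention arm of a previous trial and expects the present data to add to that evidence, so some comparison between arms is in view. The stake is a small, few-event safety table that could look less favourable to the intervention than the truth.

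**Working it through.** The protocol gives no SAE rate and no capture probability, so there is no figure of its own to reproduce. All capture and risk values below are assumptions.

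**Inputs from the protocol.** Seven coaching sessions (10.1). 30 per arm against 21 needed (12.2), a loss allowance of 1 − 21/30 = 0.30. This is a sample-size buffer, not a forecast of missing SAE data.

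**Model 1: loss to follow-up only.** A share d drops out evenly over 20 weeks, SAE risk is constant and equal in the two arms, dropouts give no week-20 report, and coaching reveals every SAE up to the point of leaving.

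- Control capture = 1 − d
- Intervention capture = (1 − d) + d/2 = 1 − d/2
- Recorded ratio = (1 − d/2)/(1 − d)

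| d | Control | Intervention | Ratio | Gap |
|---|---|---|---|---|
| 0.10 | 0.90 | 0.95 | 1.06 | 0.05 |
| 0.20 | 0.80 | 0.90 | 1.13 | 0.10 |
| 0.30 | 0.70 | 0.85 | 1.21 | 0.15 |

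**Model 2: imperfect week-20 capture as well.** Let a be the share with week-20 data, w the sensitivity of that record, and q the chance that an SAE reaches the team earlier through intervention-only contacts.

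- Control capture = a·w
- Intervention capture = 1 − (1 − q)(1 − a·w)

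| a | w | q | Control | Intervention | Ratio |
|---|---|---|---|---|---|
| 1.00 | 1.0 | any | 1.000 | 1.000 | 1.00 |
| 0.85 | 0.9 | 0.3 | 0.765 | 0.836 | 1.09 |
| 0.85 | 0.9 | 0.9 | 0.765 | 0.977 | 1.28 |
| 0.70 | 0.9 | 0.3 | 0.630 | 0.741 | 1.18 |
| 0.70 | 0.9 | 0.9 | 0.630 | 0.963 | 1.53 |

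**In events.** At an assumed true risk of 5% to 10%, 30 per arm gives 1.5 to 3 SAEs per arm.

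- Model 1 at d = 0.30: 0.15 × 1.5 = 0.23 to 0.15 × 3 = 0.45 of an event.
- Model 2 at a = 0.70, w = 0.9, q = 0.9: 0.333 × 1.5 = 0.5 to 0.333 × 3 = 1.0 event.
- Worst corner tried (a = 0.70, w = 0.7, q = 0.9; captures 0.490 and 0.949) at 10% risk: 0.459 × 3 = 1.4 events.
- For Model 1 to shift one whole event, 1/0.15 = 6.7 SAEs per arm are needed, a risk of 6.7/30 = 22% in 20 weeks.

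**After the fix.** With one common ascertainment as the only source compared, q = 0 and the ratio is a·w/(a·w) = 1.00, provided a and w are the same in both arms.

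**The case against.** The best defence is that section 11 already makes the week-20 record, taken for all participants, the analysed source, and that section 11.2 concerns reporting. On that reading, complete week-20 capture leaves the count untouched by early awareness, which changes only the date of recording. This is a fair reading, but the text does not settle it: section 11.2 tells the team to record any SAE, not just the reportable ones, and section 11 says prospective recording will not happen.

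Further points stand:

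- Coaches have no stated duty to ask about SAEs or pass them to the research team. Their channel runs to the practice, and the recordings are sent for fidelity checks. Full capture through coaching is an upper bound.
- A reader might infer that a control who drops out contributes no SAEs. The protocol does not say so. It names no source for non-attenders, but section 13.1 lists hospital records among source documents, section 13.2 gives the follow-up practitioner access to clinical notes, and section 10.7 seeks to retain people who stop treatment. Silence is a gap, not proof of zero capture.
- Controls also have the week-12 link and usual care, so week 20 is their only stated SAE collection point, not their only contact.
- SAEs are not listed outcomes (section 6), have no test specified in section 12.1, and play no part in the decision rule (section 12.3).

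**Conclusion.** The conflict between sections 11 and 11.2 is real, and so is the unequal access to interim awareness. The conclusion is conditional: if awareness-based records enter the by-arm summary, ascertainment is unequal and the likely direction is against the intervention.

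A reader might go further and infer that the SAE comparison is biased, or that unseen control admissions would reverse its direction. The documents do not support that. The recorded ratio is 1.00 if week-20 capture is complete. It is 1.06 to 1.21 at 10% to 30% loss if coaching reveals every SAE before dropout, and higher only if week-20 sensitivity is also imperfect and interim capture is substantial. At an assumed 5% to 10% risk this is typically less than one event, and with so few events a change of direction would arise mainly from chance. No test or go/no-go decision described in the protocol depends on it. The point is modest but worth correcting, because SAE capture belongs in the protocol and the correction is cheap.

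**What to change.** Reconcile sections 11 and 11.2, and say which records serve which purpose.

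- **Comparison between arms.** Use one retrospective ascertainment covering randomisation to week 20, on the same form and by the same method in both arms. The practice completes it from the GP record for every participant who has not withdrawn consent for data use, whether or not they attend at week 20.
- **Ethics committee reporting.** Keep the awareness route in section 11.2 for this purpose.
- **SAEs known only through intervention-arm contacts.** Still report them, flagged by source and shown separately from the like-for-like comparison, so that no real event is dropped from the safety summary.

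The cost is a brief record check for 60 people at the 5 participating practices, one paragraph of protocol text, and consent wording that covers the check. One limit remains: coach-to-practice communication may make the GP record itself somewhat fuller in the intervention arm, so equal sensitivity is still an assumption, though a weaker one than the present text requires.

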12. STATISTICS AND ANALYSIS

12.1. Description of Statistical Methods

The primary outcome of differences in weight loss will be assessed using a generalised linear mixed model, with participant and time included as random effects and included fixed effects for duration of diabetes (\geq /< 6 years) as a binary variable and trial arm. The treatment effect will be given by the treatment by time interaction, using post-estimation commands.

Secondary outcome measures for this study include other clinical outcomes: HbA1c, total cholesterol, LDLcholesterol, HDL, triglycerides, blood pressure, and changes in diabetes and blood pressure medications. These will be analysed by analogous generalised linear mixed models with link functions appropriate for the type of data, with the same variables included and following the same procedure to assess the effect of the intervention.

We will also report process outcomes including recruitment rates and fidelity to the dietary intervention to understand whether aspects of the recruitment process and intervention could be modified.

Qualitative data from telephone interviews will be analysed thematically following a content analysis approach (11). Participant experience questionnaires will be analysed using simple summary statistics and reported descriptively.

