7. STUDY DESIGN

This proof of concept trial will be an individually randomised controlled trial, performed in adult patients with type 2 diabetes and a BMI over 27 kg/m² (where individuals are from White ethnic groups) or over 25 kg/m² (where individuals are from Black, Asian and other ethnic groups). Participants will be randomly assigned to either the intervention group (eDIAMOND programme) or the control group (NHS usual care). Due to the nature of the intervention, it will not be possible to blind the participants, clinicians delivering the intervention, or some of the study team to the treatment allocation.

Briefly, the eDIAMOND programme will consist in a low-carbohydrate, low-energy diet intervention which will be 12 weeks of support for weight loss, and 8 weeks of weight maintenance support. Online support from health coaches will be available throughout the programme.

All participants from both groups will be enrolled for 5 months from randomisation to final follow up. Data collection will be in the form of clinical and biochemical measurements (Weight, HbA1c, cholesterol). A schematic of the study is included in appendix A.

This is an individually randomised controlled trial. Participants will be recruited via GP practices and randomised 1:1 with simple randomisation, stratified by T2D duration (\geq /< 6 years), to either the intervention group or control (usual care). They will be enrolled in the study for 5 months. Most study procedures will be conducted online or remotely by telephone or via video calls by Microsoft Teams/Zoom if participant prefers. If by Microsoft Teams/Zoom, the coach will call the participant at the time of the appointment and the coach and participant will be able to talk and see each other via the camera (if participant prefers)) including: screening, eligibility assessment, informed consent, randomisation, engagement with the remote intervention. Participants will be asked to attend 2 face to face appointments for the research study at their local GP practice for measurements to be taken (weight, blood pressure) and blood tests, at baseline and 20 weeks (5 months) post randomisation. Face to face appointments will be incorporated with routine clinical appointments when possible.

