8.3. Exclusion Criteria

- Currently diagnosed with type 2 diabetes but who are in remission using the NHS diabetes remission criteria, or who are recorded as not on diabetes medication and whose HbA1c levels on enrolment are <48mmol/mol at baseline
- Currently using insulin injections
- GLP1-agonists or SGLT2 inhibitors started in the six months prior to study enrolment
- Diagnosed with a known eating disorder for whom the programme could be unsafe or require extensive monitoring to ensure safety
- People who are pregnant or planning pregnancy
- People who are breast feeding
- Diagnosed with a myocardial infarction or stroke in the past three months, or uncontrolled cardiac conduction abnormalities e.g. long QT syndrome.
- Currently diagnosed with maculopathy or proliferative retinopathy
- People with HbA1c ≥87mmol/mol
- People with significant life-limiting illnesses that mean that remission is unlikely to improve health (severe cardiac failure, palliatively treated cancer, dementia), or other current severe illness
- Planned major surgery that means that following a weight loss programme would not be possible.
- People taking part in other research that would compromise either their participation in eDIAMOND or the other research study/ies that they are participating in.
- Taking part in or planning to take part in the NHS Pathway to Remission programme.

NB: If the patient is taking warfarin, they are not excluded from participating in the study, but will be advised to inform their local monitoring service about their participation, and they may be advised to have additional blood test monitoring of their INR as part of their care.

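### Section 12.1 makes time a random effect with no fixed time term, so the treatment by time interaction takes in some or all of the control arm's own weight change

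*Protocol*

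**What the plan says.** Protocol section 12.1 assigns a role to each term in the primary model. It is a generalised linear mixed model "with participant and time included as random effects and included fixed effects for duration of diabetes", the latter entered "as a binary variable and trial arm". Participant and time are therefore random; diabetes duration and arm are fixed. The next sentence names the estimator: "The treatment effect will be given by the treatment by time interaction, using post-estimation commands". Neither a fixed time term nor the interaction itself is in the list of fixed effects.

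The other clinical outcomes named in 12.1 (HbA1c, lipids, blood pressure, and changes in diabetes and blood pressure medication) get analogous models "with the same variables included and following the same procedure to assess the effect of the intervention".

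Section 7 places the face-to-face measurements "at baseline and 20 weeks (5 months) post randomisation". Section 10.3 agrees: week 12 brings only a food questionnaire, and weight is next measured at week 20. Section 12.2 plans for control weight to change: "Assuming a mean weight loss of 5kg in the intervention arm and 1kg in the control arm", "both with a standard deviation of 3.5 kg".

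**The concern.** An arm by time coefficient equals the difference between arms in mean change only if a separate fixed time term carries the control arm's mean change. Random effects have mean zero, so they cannot fully do that job. Where time is random and the control arm loses weight, some or all of that loss is credited to the intervention.

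Section 12.3 says the team will consider a fully powered remission trial if weight loss is significantly greater in the intervention arm than in control. An estimate that includes control weight loss does not test that statement, and its error favours the intervention in the situation that section 12.2 expects.

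**Working it through.** **Inputs.** From section 12.2: mean loss 5 kg (intervention) and 1 kg (control), SD of change 3.5 kg, 21 per group needed, 30 recruited. From sections 7 and 10.3: two trial weights per person. Assumptions for the simulations: complete data, a baseline SD of 15 kg, two-sided 5% tests.

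**The plan's own sample size.** Section 12.2 states neither alpha nor power. With two-sided 5% and 95% power, n = 2 × (1.96 + 1.645)² × 3.5² / 4² = 19.9, so 20 per group. The exact t calculation gives 21 (power 95.1%). The figure of 21 reproduces on those assumptions and is not affected by this point.

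**Algebra.** Let dI and dC be the observed mean losses in the intervention and control arms.

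- *Fixed time and arm by time, participant random intercept:* interaction = dI − dC. Expected value 5 − 1 = 4.0 kg.
- *No common time term, or only zero-mean participant slopes:* the control mean is held flat, so interaction = dI. Expected value 5.0 kg.
- *Time as a crossed random effect with two levels:* interaction = dI − k·dC, with k = max(0, 1 − SE²/dC²) and SE = 3.5/√n, the standard error of one arm's mean change (0.764 at n = 21, 0.639 at n = 30). Averaged over the sampling distribution of dC (mean 1 kg), this gives 4.37 kg at n = 21 and 4.32 kg at n = 30. The time variance is estimated as zero whenever |dC| < SE. At n = 21 the probability is Φ(−0.309) − Φ(−2.309) = 0.37; at n = 30 it is Φ(−0.565) − Φ(−2.565) = 0.28. In those trials the whole control change enters the interaction.

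**Simulation (REML, 1,000 trials per cell, Wald test at 1.96).**

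| Model | Mean effect, 5 v 1 kg (n = 21 / 30) | False positives, both lose 1 kg (n = 21 / 30) |
|---|---|---|
| Fixed time | 4.04 / 4.03 kg | 5.7% / 6.0% |
| Crossed random time | 4.35 / 4.32 kg | 15.0% / 13.9% |
| No common time term | 5.02 / 5.00 kg | 23.8% / 32.4% |

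A separate simulation of 200,000 trials per scenario gave 13-14% for the crossed model, and 23% and 32% with no common time term.

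**Hand check of the last row.** With both arms losing 1 kg, the fitted variance of change averages 3.5² in the intervention arm and 3.5² + 1² in control: (12.25 + 13.25)/2 = 12.75. At n = 21 the model standard error is √(12.75/21) = 0.779, so rejection needs dI > 1.96 × 0.779 = 1.527. The probability is 1 − Φ((1.527 − 1)/0.764) = 1 − Φ(0.690) = 24.5%. At n = 30 the threshold is 1.278 and the probability is 1 − Φ(0.435) = 33.2%. Both agree with the simulation.

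**No control change.** With a true difference of 4 kg and flat controls, all three models average 3.98 to 4.03 kg. The bias needs a non-zero control change.

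**Identifiability, as a note.** Two weights per person give three distinct covariance elements (two variances and one covariance). A random intercept, a random slope, their covariance and a residual are four parameters, so that reading cannot be fitted uniquely. Once time is fixed, the arm by time contrast depends only on the variance of change, which is estimable.

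**The case against.** The best defence is that the list in 12.1 is shorthand. The interaction is not among the listed fixed effects either, yet it must be in the model, so an analyst might enter the full arm by time factorial and contrast it by post-estimation. That gives 4.0 kg, and a SAP may set it out. This shows that the fault could be harmless in practice. It does not rescue the text, because 12.1 does not leave time unmentioned: it names time as random. The correct analysis needs a fixed term that the section does not list.

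The size also depends on how time is made random. The 5.0 kg and 23-32% figures belong to the less favourable reading. The crossed reading gives about a third of that bias, so the range has to be quoted.

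Several stronger inferences are tempting but not supported:

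- *An inestimable model for remission.* Section 8.3 excludes people "who are recorded as not on diabetes medication and whose HbA1c levels on enrolment are <48mmol/mol at baseline", so no one should meet the remission definition at baseline, and a logistic arm by time interaction would break down. But 12.1 does not name that outcome among those it models, nor the wellbeing and diabetes-distress scores, so no such fit is specified.
- *A change-score comparison as an error.* It is valid under randomisation. Baseline adjustment multiplies the variance by (1 + ρ)/2, which for weight is 0.975 to 0.99 at an assumed ρ of 0.95 to 0.98.
- *Error rates of 67-84%.* These need both the less favourable reading and a 2 kg loss in both arms, which the documents do not assume. The crossed reading gives 11.6-13.3% in that case.
- *A binding decision rule.* Section 12.3 says only that a further trial will be considered.

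**Conclusion.** The point stands for the model as written. With time random and no fixed time term, the interaction overstates the intervention effect whenever controls lose weight. Under section 12.2's assumptions the overstatement is about 0.3 to 0.4 kg (crossed random time) or 1.0 kg (no common time term, or only zero-mean participant slopes) on a true 4.0 kg. If both arms lose 1 kg, false positives are about 13-15% or 23-32%, against about 5-6% with fixed time. These figures rest on complete data and the plan's SD of 3.5 kg. There is no bias if mean control weight is unchanged, and none if the analyst adds the fixed time term that 12.1 omits. The sentence specifies the primary estimator, so it should be corrected before analysis.

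**What to change.** Reword section 12.1 so that time (week 20 against baseline) and arm by time are fixed effects alongside arm and diabetes-duration stratum, with a participant random intercept and no random time effect. The treatment effect is then the arm by time coefficient. Equally acceptable is a linear regression of week-20 weight on arm, baseline weight and duration stratum, with the arm coefficient as the effect.

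Make the same correction to the analogous secondary models that 12.1 names, and carry the wording into the SAP if there is one. The cost is a text amendment: no new data, participants or visits, and no change to the sample size.

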9.4. Baseline Assessments

All participants from both groups (intervention and control) will complete a 2-part baseline assessment, firstly online and then at their GP practice.

9.4.1. Online:

Participants will be asked to complete a baseline questionnaire requesting demographic information and their current medication, and the standard questionnaires that will be used in the study (the Problem Areas in Diabetes (PAID) score, the WHO 5 (quality of life assessment), and a food intake questionnaire ("Oxford WebQ Questionnaire", where participants are asked to record all food and drink intake in the last 24 hours (10)). This questionnaire will also further assess whether people are willing to complete online trial procedures, and only those who complete all three questionnaires will be randomised. Participants will be informed in the Participant Information Sheet that they will only be able to enter the study after completing each individual questionnaire fully in one attempt as the system will not allow them to go back into each questionnaire to answer the remaining questions later. There are four questionnaires for each participant to complete and should take less than 35 minutes in total. Patients will be able to fill in the baseline questionnaires at any time after complete each questionnaire in one attempt. Should a participant not complete their questionnaires, reminder emails will be sent at one and two weeks after they received the initial invite to complete the questionnaires.

9.4.2. At the GP practice:

Having completed the online assessment, participant details will be passed to the GP practice (or practice representative in the clinical research network) to book the in-person component of their baseline assessment at their GP practice for measures which cannot be conducted online. At this appointment (with a clinical research network nurse, practice nurse or healthcare assistant), their height, weight and blood pressure will be measured and recorded, and a blood sample taken (approx. 9 ml) for baseline values (HbA1c, blood pressure, total cholesterol, LDL-cholesterol, HDL). Once these results are returned, they will be entered into the CRF. Participants who are recorded as not on diabetes medication and whose HbA1c

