10.4 Sample Handling

Blood samples for 2 sets of tests (HbA1c and lipid profile (total cholesterol, LDL-cholesterol, HDL, triglycerides)) will be taken from all participants from both groups, at the 2 specified visits at their GP practice (baseline and 20 weeks), with an approximate maximum total volume of 9ml. All blood samples will be taken, handled, analysed and disposed of according to standard NHS procedures and local practice policy. The samples will be sent to NHS laboratories for analysis and results reported to the GP following standard procedures. Blood samples will not be stored after analysis.

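### For HbA1c, blood pressure and lipids, the model in section 12.1 amounts to comparing unadjusted change scores; using the baseline already collected would give more precise estimates at no cost

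*Protocol*

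**What the plan says.** Section 12.1 describes a generalised linear mixed model for weight, "with participant and time included as random effects and included fixed effects for duration of diabetes" (split at 6 years) "as a binary variable and trial arm". The estimator is then named: "The treatment effect will be given by the treatment by time interaction, using post-estimation commands". HbA1c, lipids, blood pressure and medication changes get analogous models, "with the same variables included and following the same procedure to assess the effect of the intervention".

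The clinical measurements are taken twice. Section 7 places weight, blood pressure and blood tests "at baseline and 20 weeks (5 months) post randomisation", and section 10.4 schedules HbA1c and the full lipid profile at the same two visits. Section 9.4.2 covers the pre-randomisation visit: "their height, weight and blood pressure will be measured and recorded, and a blood sample taken".

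The protocol nowhere lists the baseline value as a covariate, and nowhere states that the arms share a common baseline mean.

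**The concern.** With one baseline and one follow-up value, an arm-by-time interaction exists only if baseline is one of the outcome rows. Because arm also has its own main effect, the model estimates a separate baseline mean in each arm. All baselines are taken before randomisation, so the true means are equal. Estimating a difference known to be zero uses up information, and subtracting the whole observed baseline difference over-corrects whenever the correlation is below 1.

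What is at stake is the width of the confidence intervals for HbA1c, blood pressure and lipids in a 60-person trial. HbA1c matters most, because section 12.3 names remission of type 2 diabetes as the target of any later full trial.

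**Working it through.** **1. The plan's own figure.** Section 12.2 gives a 4 kg difference, SD 3.5 kg and 21 per group. It states no alpha or power. At an assumed two-sided 5%, the two-sample t calculation gives 13.1, 17.1 and 20.9 per group for 80%, 90% and 95% power, so 21 corresponds to 95%. Recruiting 30 to keep 21 implies 30% loss (30 × 0.70 = 21). This sample size does not depend on the present point.

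**2. What the interaction estimates.** Section 12.1 lists time only as a random effect. I read it in the usual form: fixed arm, time and arm-by-time, with a participant random intercept. Let D0 and D20 be the between-arm differences in observed means at baseline and week 20. The arm term fits D0, and arm plus interaction fits D20, so the interaction is D20 − D0, the difference in mean change. In simulated complete-data trials (600 per setting, 30 per arm, duration included) the two agreed to about 3e-15.

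**3. Precision with complete data and equal SDs.** With common SD σ, correlation ρ and n per arm:
- planned: Var(D20 − D0) = (2/n)σ² × 2(1−ρ)
- baseline-adjusted: Var(D20 − ρD0) = (2/n)σ² × (1−ρ²)
- ratio adjusted/planned = (1+ρ)/2

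| ρ (assumed) | Ratio | Variance cut | SE cut |
|---|---|---|---|
| 0.3 | 0.65 | 35% | 19% |
| 0.5 | 0.75 | 25% | 13% |
| 0.7 | 0.85 | 15% | 8% |
| 0.9 | 0.95 | 5% | 2.5% |

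The simulated ratios were 0.77 (ρ = 0.5) and 0.90 (ρ = 0.7) for a week-20 model adjusted for baseline, and 0.76 and 0.87 for the mixed model with a common baseline mean. These include simulation error and, for the former, one lost degree of freedom.

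**4. Unequal SDs.** Let k be baseline SD divided by week-20 SD. The ratio becomes (1−ρ²)/(1+k²−2ρk). The denominator exceeds the numerator by (k−ρ)², so adjustment never loses apart from the degree of freedom. The gain shrinks as k falls from 1 towards ρ. At ρ = 0.7:
- k = 0.9: 0.51/0.55 = 0.93
- k = 0.8: 0.51/0.52 = 0.98
- k = 1.1: 0.51/0.67 = 0.76

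**5. Dropout.** Suppose 30 per arm have a baseline and 21, missing at random with respect to outcome, have week 20 (equal SDs). Per arm, in units of σ²:
- planned: (1−ρ²)/21 + (1−ρ)²/30
- common baseline mean: (1−ρ²)/21
- ρ = 0.5: 0.0357/(0.0357 + 0.0083) = 0.81
- ρ = 0.7: 0.0243/(0.0243 + 0.0030) = 0.89

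The simulation with 30% missing gave 0.79 and 0.93 for the week-20 model, and 0.76 and 0.90 for the common-baseline model. Allowing for simulation error, both routes point to a cut of roughly a fifth at ρ = 0.5 and a tenth at ρ = 0.7. The planned estimate stayed close to the change score (SD 0.307 against 0.310 at ρ = 0.5).

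**6. Weight.** If 3.5 kg is the SD of change, ρ = 1 − 3.5²/(2 × SD²). Assumed weight SDs of 12, 15 and 20 kg give ρ = 0.957, 0.973 and 0.985. With 21 per arm, power moves from 95.1% to 95.5%, 95.3% and 95.2%.

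**The case against.** The planned contrast is valid. It is unbiased under randomisation and matches outcomes declared as changes. The protocol claims no power for any secondary outcome, so any power figure for them is hypothetical. Section 12.3 ties progression to weight alone, where the gain is negligible. For HbA1c, equal SDs are doubtful: section 8.3 excludes baseline values of 87 mmol/mol or more, and those below 48 in people off medication, while week-20 values are unrestricted. Exact parameterisation is often left to a statistical analysis plan.

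Most of this stands and limits the point. Three stronger readings that a reader might infer are not supported:
- **That the result would be biased or the trial's decision at risk.** Neither follows, since the loss is of precision only and the progression rule uses weight.
- **That the secondary outcomes decide whether a full trial proceeds.** Section 12.3 does not say so.
- **That adjustment guarantees a set power gain.** An effect with 80% power under the plan would reach about 86% at ρ = 0.7 with complete data and equal SDs. It reaches only about 83% at the simulated ratio of 0.93 under 30% loss.

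Two parts do not stand. Section 12.1 names the variables and the estimator, so this is a stated choice, and no reading of the listed terms adds baseline adjustment. Nor does declaring the outcome as a change require the unadjusted contrast: once baseline is a covariate, modelling the change or the week-20 value gives the same arm coefficient.

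**Conclusion.** The point holds as a free improvement in efficiency, not as the correction of an invalid analysis. For continuous outcomes under an identity link, section 12.1 compares unadjusted change scores and gives up precision that the scheduled baseline measurements could supply. The variance cut available is about 25% at ρ = 0.5, 15% at 0.7 and 5% at 0.9 with complete data and equal SDs. It is nearer a fifth and a tenth at ρ = 0.5 and 0.7 with 30% missing, and less again if the baseline SD is modestly smaller than the week-20 SD. All of this rests on assumed correlations, as the protocol gives none. The benefit lies in the secondary estimates, notably HbA1c. The identity does not carry over to outcomes modelled with other link functions.

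**What to change.** Amend section 12.1 for the continuous outcomes.

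- **Preferred:** keep the mixed model and constrain the arms to a common baseline mean, with fixed time, arm-by-time and the duration stratum but no arm main effect. This keeps participants with a missing week-20 value in the model. Letting the SD differ between the two times avoids relying on equal variances.
- **Alternative:** model the week-20 value with its baseline value, arm and duration stratum as covariates.

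Use the same form for weight, for consistency. The cost is a few words in the protocol, carried into any analysis plan. It needs no new data or visits, since section 10.4 already schedules the bloods, including triglycerides, at both visits, and it does not change the sample size.
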